- 13. The uptitration phase between Visit 2 and Visit 3 can be extended by a maximum of 6 days if the patient needs longer to uptitrate or to achieve 7 consecutive stable days at full dose.
- 14.
- 15. At Visit 4 (PK FU) the optional nintedanib Named Patient Programme will be discussed with the patient.
- 16. AEs and concomitant therapy should be checked at regular intervals during the PK days.
- 17. At Visit 2 Day 2 and Visit 3 Day 24 only these procedures need to be done see Section 6.2.2.
- 18. The PK Follow Up visit should occur at least 28 days after last drug intake.
- 19. DLCO testing will be performed once at visit 1 or 2, or during the screening period (visit 1 to visit 2). The results will be corrected for haemoglobin by the site, see section 10.3 for further details.

Page 8 of 118

Proprietary confidential information © 2016 Boehringer Ingelheim International GmbH or one or more of its affiliated companies

FLOW CHART - GROUP 2

Trial Periods	Screening Period ¹	PK ev	aluation pe	eriod ⁹	PK Follow- up Period ¹⁶
Visit	1	2	3 a	3b ¹²	4
Weeks		0	1	2	6
Days	-28 to -1	1	8	16 ¹⁰	44
Time window for visits			+3 days	+3 days	+3 days
Informed consent ²	Х				
Demographics	Х				
Medical history	Х				
Review of in-/exclusion criteria	Х	Х			
Drug and alcohol testing at site	Х	Х			
Physical examination	Х	Х	Х	Х	Х
Vital signs ³	Х	Х	Х	Х	Х
Laboratory tests	Х		Х	Х	Х
Pregnancy test (urine) ⁸	Х	Х	Х	Х	Х
PK sample ⁶			Х	Х	
		Х			
		Х	X ¹³	X ¹³	Х
		Х	X ¹³	X ¹³	
	Х				Х
Spirometry ¹¹	Х	Х	Х	Х	Х
DLCO ¹⁷	Х	$(X)^{17}$			
Register screening / start of treatment	Х	Х			
Dispense trial drugs ⁴		Х	Х	Х	
Collect trial drug & compliance check			Х	Х	
Dispense and/or collect & review diary ⁵		Х	Х		
AEs and Concomitant medication ¹⁵	Х	Х	Х	Х	Х
Conclusion of PK evaluation period				Х	
Conclusion of subject participation					X ¹⁴

FOOTNOTES – GROUP 2

- 1. The screening period between Visit 1 and 2 should last a maximum of 28 days. Eligible patients can be started on treatment once central lab results have been received and are found to be consistent with eligibility criteria.
- 2. At site discretion, informed consent may be obtained on one day and the remainder of the screening procedures can follow.
- 3. Vital signs to include blood pressure, pulse rate and weight.

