6.2.3 Follow Up Period and Trial Completion

A minimum of 28 days after the end of treatment all patients who started treatment are asked to come for a final follow up visit.

Follow up visit:

Assessments at this visit include:

- Physical examination and vital signs.
- •
- Urine sample for pregnancy test for women of childbearing potential.
- ECG.
- Review concomitant therapy and any adverse events.
- Spirometry.
- At the end of this visit the patient will have concluded their time in the trial.

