6.7 BASELINE, TIME WINDOWS AND CALCULATED VISITS

As a general rule, last assessment before first trial drug intake (included) will be used as baseline. If the baseline value is missing and the screening value is available, then the baseline value will be defined as the screening value taken closest to baseline date.

A windowing will be performed as described in Tables 6.7: 1, 6.7: 2, 6.7: 3 and 6.7: 4, in order to assign data to the relevant study visit based on the actual day of the assessment. Data will be analysed using the re-calculated visits in the statistical tables. However, in the listings, all visits performed will be displayed (even if outside time-window), along with the re-calculated visit.

Table 6.7: 1 Time windowing rules for physical examination, vital signs - Group 1

Time window of actual day ^[1]			Allocated to		
Start day	End day (included)	Length of the time-window [days]	Visit number	Visit name	Planned day of the visit
1	1	1	1, or 2 ^[2]	Baseline	1
2	29	28	3	3 weeks	23
30	Last treatment intake + 27 ^[3]	variable	NA	Between 3 weeks - FU	NA
Last treatment intake + 28	Last treatment intake + 31	4	4	Follow-up	52

[1] First trial drug intake date is taken into account as a reference to calculate time windows

[2] Depending on the last assessment before first trial drug intake (included), refer to Section 6.7 for baseline definition

[3] This period only exists if last treatment intake occurs after 2 days (later than 28 days before 30 days)

Table 6.7: 2 Time windowing rules for physical examination, vital signs - Group 2

Time window of actual day ^[1]			Allocated to		
Start day	End day (included)	Length of the time-window [days]	Visit number	Visit name	Planned day of the visit
1	1	1	1, or 2 ^[2]	Baseline	1
2	12	11	3a	1 week	8
13	19	7	3b	2 weeks	16
20	Last treatment intake + 27 ^[3]	variable	NA	Between 2 weeks - FU	NA
Last treatment intake + 28	Last treatment intake + 31	4	4	Follow-up	44

[1] First trial drug intake date is taken into account as a reference to calculate time windows

[2] Depending on the last assessment before first trial drug intake (included), refer to [Section 6.7](#) for baseline definition

[3] This period only exists if last treatment intake occurs after 6 days (later than 28 days before 20 days)

Table 6.7: 3 Time windowing rules for laboratory measurements – Group 1

Time window of actual day ^[1]			Allocated to		

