Start day	End day (included)	Length of the time-window [days]	Visit number	Visit name	Planned day of the visit
1	1	1	1	Baseline	1
2	38	37	3	3 weeks	23
39	No upper limit	NA	4	Follow-up	52

[1] First trial drug intake date is taken into account as a reference to calculate time windows

Table 6.7: 4 Time windowing rules for laboratory measurements – Group 2

Time window of actual day ^[1]			Allocated to		
Start day	End day (included)	Length of the time-window [days]	Visit number	Visit name	Planned day of the visit
1	1	1	1	Baseline	1
2	12	11	3a	1 week	8
13	30	18	3b	2 weeks	16
31	No upper limit	NA	4	Follow-up	44

[1] First trial drug intake date is taken into account as a reference to calculate time windows

If after windowing of visits at baseline, two values fall within the same baseline interval, then the last value will be taken into account. If after windowing of post-baseline visits, two visits fall in the same interval, then the measurement closest to the planned visit will be taken into account. In case two measurements are equidistant from the planned visit, then the last one will be picked. The same rules will be applied for laboratory measurements.

For physical examination and vital signs only, if after windowing of post-baseline visits, two values fall within the same interval “Follow-up” then only the first value will be taken into account.

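### SAP laboratory windows count from first intake, so an early stopper's follow-up lab can be filed as Visit 3, and only one of that patient's two labs is then tabulated

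*SAP*

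**What the plan says.** **SAP 6.7, laboratory tables (6.7:3 and 6.7:4).** Both carry the note "First trial drug intake date is taken into account as a reference to calculate time windows". In Group 1 the Visit 3 row reads "2 38 37 3 3 weeks 23" (start day, end day, length, visit number, name, planned day) and the follow-up row reads "39 No upper limit NA 4 Follow-up 52". In Group 2, Days 13 to 30 are Visit 3b and Day 31 onward is Follow-up.

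**SAP 6.7, physical examination and vital signs (6.7:1 and 6.7:2).** Here the Follow-up row starts at "Last treatment intake + 28" and ends at last intake + 31. A separate row takes the days between the last treatment visit and follow-up.

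**SAP 6.7, two values in one post-baseline window.** In that case "then the measurement closest to the planned visit will be taken into account", and the later value is used if the two are equally distant. Statistical tables use the re-calculated visit; listings show every visit performed.

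**Protocol.** Footnote 18 to the Group 1 flow chart says "The PK Follow Up visit should occur at least 28 days after last drug intake". Section 6.2.3 extends this to early stoppers: "all patients who started treatment are asked to come for a final follow up visit". Under sections 4.1.4 and 4.2.1, patients who stop early still return for Visit 3 (Group 1) or Visit 3b (Group 2). The flow charts mark laboratory tests at those visits and at Visit 4.

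**The concern.** The laboratory cut-offs fit a patient who completes treatment. For a patient who stops early, the follow-up visit moves forward with the last dose but the window does not. The follow-up lab can then land in the Visit 3 window, with two effects.

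- One clinic visit carries two labels: Follow-up for vital signs and 3 weeks for laboratory data.
- If a Visit 3 lab was also taken, both values compete for one cell. The loser disappears from the statistical tables and the patient's Follow-up entry is empty.

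The protocol synopsis names change from baseline in laboratory parameters as a safety criterion. Patients who stop early, often for intolerance, are those whose laboratory course a reader will want to see correctly labelled. With 16 patients planned in Group 1, one substituted value can alter a reported minimum or maximum.

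**Working it through.** **1. The SAP's own figures reproduce.** Length = end − start + 1: Group 1 Visit 3, 38 − 2 + 1 = 37; Group 2 Visit 3b, 30 − 13 + 1 = 18. The cut-offs are midpoints of the planned days: (23 + 52)/2 = 37.5, hence Day 38; (16 + 44)/2 = 30. So they presume last intake on schedule.

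**2. Inputs.** L = day of last intake (first intake = Day 1). The follow-up lab is on Day L + d. The protocol gives d ≥ 28. The flow chart's + 3 days and the vital-signs table give a nominal range of 28 to 31.

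**3. When the follow-up lab is labelled Visit 3, Group 1.** The condition is L + d ≤ 38.

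| L | Follow-up lab day for d = 28 to 31 | Filed as Visit 3 |
|---|---|---|
| 1 to 7 | latest is 7 + 31 = 38 | 4 of 4 |
| 8 | 36 to 39 | 3 of 4 |
| 9 | 37 to 40 | 2 of 4 |
| 10 | 38 to 41 | 1 of 4 |
| 11 or more | 39 or later | 0 of 4 |

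Over L = 1 to 10 that is 28 + 3 + 2 + 1 = 34 of 40 combinations. With d = 29, the spacing planned for completers (Day 23 to Day 52), the limit is L = 9.

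**4. Group 2.** The condition is L + d ≤ 30, which needs L ≤ 2 when d = 28. The value is then filed as Visit 3b, although nintedanib starts only on Day 9.

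**5. Which of two Group 1 labs is kept.** Suppose the early-stop Visit 3 lab is k days after last intake and follow-up is at L + 28. The distances from Day 23 are (L + 28) − 23 = L + 5 and 23 − (L + k). The follow-up lab is kept if L + 5 ≤ 23 − L − k, that is L ≤ (18 − k)/2.

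| k (assumed) | Follow-up lab kept for L up to | Early lab displaced, L = 2 to 10, d = 28 to 31 |
|---|---|---|
| 0 | 9 (tie at 9, later value used) | 28 of 36 |
| 1 | 8 | 26 of 36 |
| 3 | 7 | 22 of 36 |
| 7 | 5 | 14 of 36 |

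Example, L = 5, k = 1: the early lab on Day 6 is 17 days from Day 23 and the follow-up lab on Day 33 is 10 days away, so Day 33 is tabulated as 3 weeks. Vital signs from Day 33 = 5 + 28 are tabulated as Follow-up.

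If Visit 3 is instead held on Day 23, its distance is 0 and it is always kept. A follow-up lab by Day 38 is then dropped and the Follow-up entry is empty.

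**6. How many patients.** Protocol 7.7 allows for up to 4 dropouts among 16. If all 4 occurred, spread evenly over 23 days (assumption), 4 × 10/23 = 1.7 would stop by Day 10 and 4 × 7/23 = 1.2 by Day 7. Fewer or later dropouts bring this towards 0.

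**The case against.** The strongest reply is that the visit days of an early stopper are not in the readable text. The guidance is in Figure 4.1.4:1, which is not shown. Protocol 4.1.4 has a patient who fails to reach seven stable days attend Visit 3 after the 6-day extension, which suggests about Days 23 to 29. Twenty-eight days is only a minimum, and section 6.2.2 counts follow-up from Visit 3 Day 24. A patient who stops on Day 5 and is seen on Days 23 and 52 satisfies every readable rule, and both labs are filed correctly. This stands: misfiling is a consequence of the rule when follow-up comes soon enough after last intake, not a certainty for every stop by Day 10. It does not remove the defect, because follow-up at 28 days after last intake is equally within the protocol.

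A reader might also infer that drug-free values are presented as on-treatment. The documents do not support that in general. The row is called 3 weeks, and SAP 6.1 counts data up to 28 days after last intake, inclusive, as on-treatment. At exactly L + 28 only the visit label is wrong; from L + 29 the value is outside that period as well.

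Nor can one infer that the early-stop lab is routinely lost, since that depends on k, or that liver safety is obscured. The worst-value summaries in SAP 5.4.4 do not use visit windows, listings keep every visit, and clinically relevant laboratory changes are recorded as adverse events. Finally, SAP 7.8.2 refers to sponsor standards and does not set out a by-visit laboratory table. That such tables will be produced is inferred from the windowing in 6.7 and the synopsis criterion.

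**Conclusion.** The inconsistency is real and small. Group 1 follow-up labs taken by Day 38 are assigned to Visit 3. That is possible for last intake up to Day 10 and certain up to Day 7 if follow-up is 28 to 31 days after last intake. In Group 2 it is possible only for last intake on Day 1 or 2. Where a Visit 3 lab also exists, one of the two is left out of the statistical tables. It is often the early-stop lab if Visit 3 came soon after stopping (assumption), and the follow-up lab if Visit 3 was near Day 23.

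I expect 0 to 2 Group 1 patients to be affected, in descriptive by-visit laboratory tables only. The pharmacokinetic endpoints do not use these windows. The point should be corrected because the SAP already has the right anchor for vital signs and the repair is cheap; it does not threaten the trial's conclusions.

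**What to change.** In SAP Tables 6.7:3 and 6.7:4:

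1. Start Follow-up at last intake + 28, the anchor used in Tables 6.7:1 and 6.7:2. Keep the laboratory tables' open upper end; the vital-signs limit of last intake + 31 need not be copied.
2. End the Visit 3 window at the earlier of Day 38 and last intake + 27, and the Visit 3b window at the earlier of Day 30 and last intake + 27.
3. Add a Between row, as in the vital-signs tables, from Day 39 (Group 1) or Day 31 (Group 2) to last intake + 27. It exists only if last intake is Day 12 or later (39 − 27) in Group 1 and Day 4 or later (31 − 27) in Group 2. Without it, a Group 1 completer with last intake on Day 23 would have Days 39 to 50 allocated to no visit.

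With this change no lab taken at or after last intake + 28 is filed as Visit 3 or 3b, and an early-stop lab taken before then no longer competes with it. Scheduled labs of completers keep their labels (Group 1 follow-up is Day 23 + 28 = 51 or later).

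The cost is the table edits and matching programming, with no new data. Unscheduled labs in the gap move from Follow-up to the Between row.

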4.2.1.4 Management of liver enzyme elevations

Patients who experience:

- AST /ALT ≥3 ULN with signs or symptoms of severe liver damage* (including total bilirubin >2 fold ULN) or
- ALT and/or AST \geq 5 fold ULN

Should interrupt all study drugs and return to clinic for a visit 3 (Group 1) or Visit 3b (Group 2).

* Signs of severe liver damage are defined as:

- ALT/AST \geq 3 x ULN and total bilirubin \geq 2 x ULN
- ALT/AST \geq 3 x ULN and unexplained INR > 1,5
- ALT/AST \geq 3 x ULN and unexplained eosinophilia (>5%)
- ALT/AST \ge 3 x ULN and appearance of fatigue, nausea, vomiting, right upper abdominal quadrant pain or tenderness, fever and/or rash

For potential drug induced liver injury (DILI) follow up requirements please see section 5.3.7.1.

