			194:00	10:00	Glass of water	Х	Х
			195:00	11:00		Х	Х
			196:00	12:00	Glass of water, Lunch	Х	Х
			198:00	14:00		Х	Х

Footnotes Group 2

- 1. Predose PK sample can be taken prior to breakfast and administration of trial drugs.
- 2. Breakfast should consist of a continental breakfast and drug should be administered with breakfast.
- 3. On PK day 8, it is requested that the patient take their midday dose at 14:00 so that there will be a 6 hour profile. On PK day 16, this is not applicable, as the last pirfenidone dose is taken in the morning.
- 4. The last dose of pirfenidone and nintedanib during the PK evaluation period will be in the morning at 08:00.
- 5. The evening dose of pirfenidone will be taken at home. Dosing with nintedanib and pirfenidone will start on Day 9.

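### SAP Tables 6.7:2 and 6.7:4 keep Group 2's Visit 3a window open to Day 12, so an early stop visit on Days 9-12 loses its on-combination values from the by-visit tables

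*SAP*

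**What the plan says.** SAP section 6.7 assigns each assessment to a study visit by its day, counted from first trial drug intake. It then states: "Data will be analysed using the re-calculated visits in the statistical tables". Listings show every visit performed, with the recalculated visit alongside.

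The Group 2 rows give start day, end day, length, visit, name and planned day:

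- Visit 3a, in both Table 6.7:2 (physical examination, vital signs) and Table 6.7:4 (laboratory): "2 12 11 3a 1 week 8"
- Visit 3b, Table 6.7:2: "13 19 7 3b 2 weeks 16"
- Visit 3b, Table 6.7:4: "13 30 18 3b 2 weeks 16"

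Where "two visits fall in the same interval, then the measurement closest to the planned visit will be taken into account". Ties are settled as follows: "In case two measurements are equidistant from the planned visit, then the last one will be picked".

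On treatment, Protocol 10.2 (Group 2 footnotes) says: "Dosing with nintedanib and pirfenidone will start on Day 9". Visit 3a is the pirfenidone-alone visit. It is planned for Day 8, may be up to 3 days late, and is where nintedanib is dispensed (Protocol 6.2.2). Group 2 patients who stop for persistent drug-related adverse events or raised liver enzymes are sent back for Visit 3b (Protocol 4.2.1.1 and 4.2.1.4). The text gives no day for that visit.

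**The concern.** The Day 12/13 cut takes no account of the change of treatment between the two visits. From Day 9 an assessment can be an on-combination assessment, yet until Day 12 it is labelled with the pirfenidone-alone visit. It then competes with the real Visit 3a value under a rule that prefers proximity to Day 8.

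Visit 3b is Group 2's only scheduled assessment on both drugs. Vital signs are summarised only by visit and as change from baseline (SAP 7.8.3), so a value missing from that row appears in no other vital-signs summary. An early Visit 3b arises because a patient has stopped, often for intolerance, so the values at risk are not a random subset. Protocol 2.1 itself names additive adverse effects as a possibility. SAP 6.6 intends non-completers' data to be reported as far as available, and the windowing rule works against that in the tables.

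**Working it through.** **Inputs.** Windows, planned days (8, 16, 44) and selection rules: SAP 6.7. Visit 3a permitted on Days 8-11: Group 2 flow chart and Protocol 4.1.4. Nintedanib from the day after Visit 3a: Protocol 6.2.2 and 10.2. Follow-up at least 28 days after last intake: Group 2 flow chart, footnote 16. Planning allowance of up to 6 dropouts among 18 Group 2 patients: Protocol 7.7.

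**Step 1, reproduce the SAP's figures.** Length = end - start + 1. Visit 3a: 12 - 2 + 1 = 11. Visit 3b: 19 - 13 + 1 = 7 (vital signs) and 30 - 13 + 1 = 18 (laboratory). All agree. Day 12 is the midpoint of the planned days, (8 + 16)/2 = 12, and Day 30 is (16 + 44)/2 = 30. The cut is a calendar midpoint.

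**Step 2, on-combination days inside the Visit 3a window.** With Visit 3a on Day a, nintedanib starts on Day a + 1, leaving 12 - a exposed days: 4, 3, 2 and 1 for a = 8, 9, 10 and 11, which makes 10 pairings.

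**Step 3, apply the rule.** Distance = |day - 8|.

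| Visit 3a day (distance) | Later assessment by Day 12 (distance) | Value tabulated as 3a | Visit 3b |
|---|---|---|---|
| 8 (0) | 9, 10, 11, 12 (1, 2, 3, 4) | Day 8 | empty |
| 9 (1) | 10, 11, 12 (2, 3, 4) | Day 9 | empty |
| 10 (2) | 11, 12 (3, 4) | Day 10 | empty |
| 11 (3) | 12 (4) | Day 11 | empty |

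The later assessment is always further from Day 8, so it is dropped in 10 of 10 pairings and the tie rule never applies. The result is the same for laboratory values and vital signs, because the Visit 3a window is identical. Follow-up does not fill the gap: after a last intake on Day 9 it falls no earlier than Day 9 + 28 = Day 37, beyond both Visit 3b windows.

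**Step 4, the other branches.**
- If an individual Visit 3a measurement is missing, the value from Days 9-12 is kept but shown as Visit 3a.
- If the assessment falls on Days 13-19 (vital signs) or Days 13-30 (laboratory), it is allocated to Visit 3b, even if drug was stopped on Days 9-12.

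**Step 5, how many patients.** The documents give no timing for dropouts, so every line below is an assumption. The first three use all 6 allowed dropouts and Visit 3a on Day 8.
- Stops spread evenly over Days 9-15, stop visit the same day: 6 x 4/7 = 3.4.
- Stops spread evenly over Days 1-15, stop visit the same day: 6 x 4/15 = 1.6.
- As the previous line, with a two-day delay to the visit, so that only stops on Days 9 and 10 are caught: 6 x 2/15 = 0.8.
- All stop visits on Day 13 or later: 0.

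A later Visit 3a shortens the exposed period, down to one day when it falls on Day 11.

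**The case against.** The best defence is that an early Visit 3b is nowhere documented. Protocol 4.2.1.1 defers to Figure 4.1.4:1, which is not reproduced in the text available here. The one route with a stated time, failure to reach seven stable days by Visit 3b plus its window (Protocol 4.1.4), points to about Days 16-19, where nothing is lost. No laboratory test is scheduled between Visits 3a and 3b, so a stop for raised enzymes on Days 9-12 would need an unscheduled test or rest on the Visit 3a sample, which is correctly filed. A midpoint cut is conventional, and extending Visit 3a past Day 8 is needed for permitted late visits.

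Much of the safety information also survives elsewhere. Listings show all visits. Maximum liver enzyme and bilirubin elevations use the worst on-treatment value (SAP 5.4.4). Clinically relevant changes are recorded as adverse events (Protocol 5.3.8), and those leading to discontinuation have their own table (SAP 7.8.1). Physical examination has no separate analysis (SAP 7.8.5). A wholly missing Visit 3a is close to impossible for a patient on nintedanib, since the drug is dispensed there.

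All of this stands, and it limits the reach of the point. It does not remove it. The text sets no earliest day for the stop visit, so the windowing has to give a sensible answer on Days 9-12, and it does not. Allowing for a late Visit 3a does not require filing post-nintedanib values with it.

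A reader might infer that every patient who stops on Days 9-12 disappears from the tables. That does not follow: the rule acts on the assessment day and on that one value, and baseline, Visit 3a and follow-up values remain. A reader might also infer that the combination will be reported as safer than it was. The direction is plausible, but nothing in the documents measures it.

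**Conclusion.** The allocation rule is wrong for a Group 2 assessment made by Day 12 after nintedanib has started. Where a Visit 3a value exists, the on-combination value is dropped from the by-visit tables and the patient has no Visit 3b value. Where that individual Visit 3a measurement is missing, the on-combination value is shown under the pirfenidone-alone visit.

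The consequence is limited to descriptive tables, chiefly vital signs and non-liver laboratory values. PK endpoints are not affected, and no safety hypothesis is tested. The count cannot be derived: 0 to about 3 of 18 is a plausible range. Its upper end needs all 6 allowed dropouts to fall in the combination week, Visit 3a on Day 8 and attendance on the day of stopping, so it should be read as near a ceiling and not as an estimate. In a group of 18, even one or two missing values could visibly change a row. This is a modest correction worth making before the tables are programmed.

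**What to change.** In Tables 6.7:2 and 6.7:4, replace the Day 12/13 cut by each patient's first nintedanib intake:

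- **Visit 3a:** assessments from Day 2 up to and including the date of first nintedanib intake, except that an assessment recorded in the CRF as Visit 3b on that date goes to Visit 3b.
- **Visit 3b:** later assessments, up to the existing end of the window (Day 19 for vital signs and examination, Day 30 for laboratory).
- **Patients who never take nintedanib:** keep the present windows.
- **Within each interval:** keep the closest-to-planned rule.

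Including the intake date in Visit 3a protects true Visit 3a values if a patient takes the first capsule later that same day. A fixed cut after Day 8 would not do, because it would misfile permitted Visit 3a assessments on Days 9-11.

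Of the 10 pairings, the 6 with the assessment after the intake date move to Visit 3b by date. The 4 on the intake date itself move through the CRF visit label. An unscheduled assessment on that date would stay under Visit 3a, a small remaining ambiguity.

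The cost is one extra derivation and a patient-specific window. SAP 5.4.2 already needs the first nintedanib administration date for exposure, so no new data and no protocol amendment are required.
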